#### 8.2.1 Full Analysis Population

The full analysis population, also often referred to as the "intention-to-treat" population, comprises all randomised general practices and consented patients within them, regardless of eligibility error, post-randomisation withdrawal, and whether the assigned treatment was received, with sufficient or insufficient compliance. Any analyses will be based on the treatment arm assigned at randomisation, regardless of what treatment was actually received.

A subset of the full analysis population will be used to analyse the two co-primary efficacy end-points, including only the patients with the necessary data available at baseline and twelve months.

The full analysis population will also be used to analyse several secondary and exploratory end-points as outlined elsewhere in this SAP, some of which, like the primary efficacy analyses, may require data to be complete at particular time points and therefore will only include a subset of the full analysis population with the necessary data available.

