Each data point will be assumed to have an error term that is identically and independently normally distributed with constant variance. These assumptions will be checked using histograms and box plots to look at the distributional form of the primary outcome SIS scores. All assumptions for the linear mixed effects models will be assessed by viewing plots of the residual values and QQ plots. If any of the assumptions of the linear mixed model are violated then the dependent variable, SIS score, may be transformed to normality or if this fails to correct the distributional assumptions, non-Gaussian or semi/non-parametric methods for analysis will be used.

 $Y_{ijk} = \beta_0 X_{0ij} + \beta_1 X_{1ij6} + \beta_2 X_{1ij12} + u_j + \varepsilon_{ijk}$ 

The analysis population for the primary outcome will be all patients with 12-month outcome measure as the mixed effects model assumes missing at random (MAR).

For missing data analysis the following model will be fitted if there is a cluster effect:

Yijk = continuous outcome SIS score (emotion/ handicap domain)

*i* = individual patient

j = cluster/ practice

*k* = 6 month and 12 follow-up scores

 $X_1$  = dummy variable for the intervention treatment group.

X0 = baseline covariates (baseline score, gender, cluster size, time since last stroke at consent)

 $\beta_0$  = intercept which represents the average baseline SIS score for person *i* 

 $\beta_1$  = difference in score between intervention and control groups at 6 months

 $\beta_2$  = difference in score between intervention and control groups at 12 months (primary)

 $u_i \sim N_1(0, \sigma_b^2)$  is the cluster-level random practice effect

$$\begin{pmatrix} Y_{ij0} \\ Y_{ij6} \\ Y_{ij12} \end{pmatrix} \sim MuN \begin{pmatrix} \beta_0 \\ \beta_0 + \beta_1 + X_{ij6} \\ \beta_0 + \beta_2 + X_{ij12} \end{pmatrix}$$

$$\epsilon_{ijk} \sim MuN \begin{pmatrix} 0 \\ 0, \Sigma_0 \\ 0 \end{pmatrix}$$
 is the residual error, and  $\Sigma_0$  initially has an AR1 structure.

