# 11 Missing Data

The primary analysis will be the ITT participants who are in the primary analysis population. Linear mixed effects models will be used to analyse the co-primary end-points that are repeated measured. One key benefit of mixed effect models is that this type of model can include data from incomplete cases, so missing data does not necessarily preclude a subject's data from the analysis. In this instance, missing data will be dealt with using a missing at random (MAR) assumption on the analysis population. The outcome variable will include baseline, 6months and 12months outcomes. The mixed effect model will have participant id as a random effect (i.e. random baseline) and the fixed factors will be time, included as a factor variable, and treatment indicator. To help the MAR assumption the residuals of the model will be assumed to have autocorrelation (if the data allow an unstructured correlation structure stratified by treatment indicator). Additional baseline covariates will be included in the model that are potential confounders.

If there is a large amount of missing outcome data from the questionnaires, we will do a sensitivity analysis missing outcome data for the primary analysis as described in White et al. (2011) and Sullivan *et al* (2018). For each questionnaire, where guidelines exist for missing data, they will be followed (see Section 11.1).

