# **12** Sensitivity Analyses

To account for COVID-19 effects of the UK lockdown (on Monday 23rd March 202) during part of the study, a patient-level binary factor for this will be created by using the date of the 12-month assessment relative to this. As both co-primary endpoints of "emotion" and "handicap" (i.e. participation) may be affected by this event, a sensitivity analysis will be conducted by repeating the primary analyses but now including this new variable.

As a sensitivity analysis, the co-primary end-points will also be analysed under the assumption that missing data is either "missing completely at random" or "missing at random". In this instance, multiple imputation will be used to impute missing outcome data and the various potential predictors of missingness will be included in the imputation model.

Multiple imputation for cluster randomised trials should be based on a multilevel imputation model (Karla Diaz-Ordaz, 2014). For example, missing data will be imputed under different assumptions such as X=4 or X=5 and the primary analysis repeated to check the impact of this. Altering X to be different values: 5,6,7,8. Will eventually mean a "significant" result disappears and that might happen at say 7, which is the tipping point.

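### SAP 8.2.1, 10.1 and 11 conflict on who enters the repeated-measures MAR model; read literally, patients with a 6-month but no 12-month SIS score are left out

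*SAP*

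**What the plan says.** Three SAP sections define the population for the co-primary outcomes.

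- SAP 8.2.1 uses a subset of the full analysis population, "including only the patients with the necessary data available at baseline and twelve months".
- SAP 10.1 asks for a 12-month score only and offers a reason: "The analysis population for the primary outcome will be all patients with 12-month outcome measure as the mixed effects model assumes missing at random". It also sets out a model with 6- and 12-month scores as outcomes and baseline as a covariate, introduced by "For missing data analysis the following model will be fitted if there is a cluster effect". No separate population is given for it.
- SAP 11 says "The primary analysis will be the ITT participants who are in the primary analysis population" and that "missing data will be dealt with using a missing at random (MAR) assumption on the analysis population". The same paragraph gives the advantage of the method: "this type of model can include data from incomplete cases, so missing data does not necessarily preclude a subject's data from the analysis". It treats the baseline, 6-month and 12-month scores all as outcomes.

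SAP 12 adds, as a sensitivity analysis, that "multiple imputation will be used to impute missing outcome data and the various potential predictors of missingness will be included in the imputation model". SAP 11 has a further sensitivity analysis, triggered by an undefined large amount of missing outcome data. Protocol 10.2 lists multiple imputation under the analysis of the primary outcome. SAP Table 1 (section 6.5) shows that the emotion and handicap domains are collected at baseline, 6 and 12 months.

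**The concern.** A repeated-measures model helps with missing 12-month outcomes because patients who answered at 6 months and not at 12 still contribute their 6-month score. If entry requires a 12-month score, no 12-month outcome is missing among those analysed, and the only follow-up gap left is a missing 6-month score. The benefit that SAP 11 claims is then largely absent.

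The reason given in SAP 10.1 also does not support the restriction. A MAR assumption is a reason to keep partial responders, not to require the final score.

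The trial is open-label with subjective co-primary outcomes (SAP 6.3). The reasons for non-completion listed in SAP 9.1 include worsening health, burden, and finding the intervention irrelevant. Non-response after 6 months could therefore depend on how the patient was at 6 months, and could do so differently by arm. A reader of the report could take the MAR analysis as having dealt with this when it had not.

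**Working it through.** **1. The plan's own figures.** Inputs from SAP 7: 23 practices per arm, mean 20 patients, ICC 0.03, CV of cluster size 0.65, significance 2.5% (two-sided assumed), effect 0.33 SD, 20% loss. Design effect = 1 + ((1 + CV²)m − 1) × ICC.

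- m = 20: 1 + (1.4225 × 20 − 1) × 0.03 = 1.8235; effective n per arm 460/1.8235 = 252.3; power 92.8%.
- m = 16 (after loss): 1 + (1.4225 × 16 − 1) × 0.03 = 1.6528; effective n per arm 368/1.6528 = 222.7; power 89.3%.

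These normal-approximation values are close to the stated figure of at least 90% (a t version on 44 degrees of freedom gives 91.3% and 87.3%). Power is not the issue here; the inputs set the scale for what follows.

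**2. Patients affected.** 46 × 20 = 920; 0.20 × 920 = 184 without a 12-month score; 736 with one. If a fraction f of the 184 returned the 6-month questionnaire, 184f patients hold unused 6-month data. The documents do not give f, so the range is 0 to 184.

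**3. The sections side by side.**

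| SIS scores available | SAP 8.2.1 | SAP 10.1 | SAP 11, literal | SAP 11, stated benefit |
|---|---|---|---|---|
| baseline, 6, 12 | in | in | in | in |
| baseline, 12 | in | in | in | in |
| baseline, 6 | out | out | out | in |
| 12, no baseline | out | in by the population sentence, though baseline is a covariate | unclear | in if baseline is an outcome |

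The third row is the contradiction that matters. The fourth shows that 8.2.1 and 10.1 also differ from each other.

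**4. Why the restricted model adds almost nothing.** Write the likelihood as f(12-month score) × f(6-month score given 12-month score). If every analysed patient has a 12-month score, the first factor is the complete-case likelihood. With separate parameters for the second factor, a missing or present 6-month score does not change the 12-month treatment effect. Constraints such as AR1 errors or a shared baseline coefficient can move it slightly, hence essentially rather than exactly the same.

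**5. Simulation of whole trials.** 46 practices of 20, ICC 0.03, 20% loss, 120 trials per scenario, Monte Carlo SE 0.006 to 0.008. Assumptions not in the documents: AR1 correlation 0.6 between visits, dropout log-odds of 1 per SD, equal cluster sizes, known covariance, and all loss after 6 months. Estimates are in SD.

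| Dropout depends on | True effect | 12-month-only, completers | Repeated measures, completers | Repeated measures, all patients |
|---|---|---|---|---|
| nothing | 0.33 | 0.328 | 0.328 | 0.330 |
| baseline, opposite by arm | 0.33 | 0.338 | 0.338 | 0.337 |
| 6-month score, intervention arm only | 0 | 0.067 | 0.067 | 0.002 |
| 6-month score, intervention arm only | 0.33 | 0.399 | 0.399 | 0.333 |
| 6-month score, opposite by arm | 0 | 0.144 | 0.144 | 0.004 |
| 6-month score, opposite by arm | 0.33 | 0.454 | 0.454 | 0.318 |

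The two completer columns agree to three decimals in every row.

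**6. Milder dropout.** A large-sample simulation without clustering (2,000,000 patients, no true effect, correlations 0.65, 0.70 and 0.60 for 0–6, 6–12 and 0–12 months, 20% loss after 6 months) gave an absolute completer bias of 0.022 to 0.046 SD for one-arm slopes of 0.4 to 0.8 per SD. Opposite slopes of 0.8 gave 0.095 SD. Using all 6-month scores gave −0.003 to 0.002. Against the 0.33 target: 0.022/0.33 = 7%, 0.046/0.33 = 14%, 0.095/0.33 = 29%. An unadjusted SE at the planned size is about √(2/222.7) = 0.095 SD, so the one-arm bias is roughly a quarter to a half of one SE.

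**The case against.** The restrictive reading is literal but not the only one. The population sentence in SAP 10.1 may govern just the 12-month model, with the repeated-measures model standing apart. In SAP 11 the analysis population is not a defined term and could mean the full analysis population. The sentence on incomplete cases, and the use of all three visits as outcomes, suggest that the authors meant to include partial responders. This stands as far as intent goes, so the point is a contradiction to reconcile. It does not settle the text, because SAP 11 also ties the analysis to the primary analysis population, and a statistician following that would drop these patients.

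SAP 12 commits without condition to multiple imputation of missing outcomes, which returns patients without a 12-month score to the analysis. That also stands and lowers the severity. It remains a sensitivity analysis, and the 6-month score is not named among the predictors.

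A 12-month mixed model on observed outcomes is valid under MAR given its covariates, which include the baseline score. That stands too: the table shows no material bias when dropout is random or driven by baseline. What is lost is correction for missingness related to the 6-month score.

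Finally, the simulations place all loss after 6 months, while SAP 7 gives 20% as the total. Patients lost earlier have no 6-month score to recover, so the bias figures are not predictions for this trial.

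**Conclusion.** The SAP does not say consistently who enters the repeated-measures MAR model. On the literal reading that model excludes patients with a 6-month but no 12-month score and is in effect a second complete-case analysis. Two things are firm: the near-equality of the two completer analyses, and the possibility of bias if non-response depends on the 6-month score differently by arm. The size is not firm. Under assumed correlations and dropout strengths it ran from none to 0.14 SD.

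A reader might infer more than this, and the documents do not support it:

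- That nobody who withdraws is analysed. Protocol 16 has the researcher ask whether a withdrawing participant will still accept follow-up, so such a patient can have a 12-month score. The relevant group is patients without a 12-month score.
- That the plan cannot correct for dropout at all, or certainly discards the 6-month data. Baseline adjustment and the SAP 12 imputation both count against this.
- That the co-primary effects will be biased by a given share of the 0.33 SD target. No document gives the correlations or the dropout pattern.

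The change is worth making before analysis, but it is a correction of definitions rather than a flaw in the design.

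**What to change.** - In SAP 10.1 and 11, state that the repeated-measures MAR model includes all consented patients in randomised practices with a baseline score and at least one follow-up SIS score (6 or 12 months), whether or not the 12-month score was returned. This suits baseline as a covariate (SAP 10.1). If baseline is kept as an outcome (SAP 11), include all patients with any SIS score. Choose one form.
- In SAP 8.2.1 and 10.1, use one definition for the 12-month-only model and label it complete-case, valid under MAR given its covariates.
- In SAP 10.1, delete the clause that gives the mixed model's MAR assumption as the reason for requiring a 12-month score.
- In SAP 12, name the 6-month score as a predictor in the imputation model.
- Report by arm how many patients without a 12-month score contribute 6-month data.

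The cost is SAP wording. The 6-month scores are already collected and the repeated-measures model is already planned.

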# 7 Sample Size

With 23 clusters per arm and an average of 20 patients per cluster, assuming an intra-class correlation of 0.03, a typical coefficient of variation of the cluster size of 0.65 (Campbell, 2014), and 2.5% significance (adjusted to 2.5% because of the use of two co-primary outcomes), we would be able to detect an effect size of 0.33 with at least 90% power on the co-primary outcomes (emotion and handicap sub-scales of the Stroke Impact Scale (SIS v3.0)). The sample size calculation has been inflated to allow for a rate of 20% loss to follow-up for patients within clusters. Loss to follow-up of entire clusters is not anticipated.

The conservative estimate of 20 patients per practice is drawn from the trials pilot data (unpublished) and the research groups experiences of running previous trials in this population (Fletcher K, 2010; Fletcher K, 2010; O'Brien C, 2013). A typical practice with a list size of between 7,000 to 10,000 will have approximately 100 - 150 patients on the stroke register (Progress in improving stroke care, 2010). We anticipate that the electronic search applying the exclusion criteria will eliminate around 40% of these (based on the pilot study) leaving 60 – 90 eligible patients per practice, of which about 30% will agree to take part (18 – 27 per practice). This will yield between 16 – 24 participants per practice.

The IPCAS trial was powered based upon the two co-primary outcomes (SIS emotional and handicap domains). It is important to be aware that the trial was not powered based on any secondary or exploratory end-points, and this should be considered in particular when interpreting any resulting p-values.

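### SAP 10.1 and 11 conflict on whether baseline SIS is an outcome, a covariate or both in the repeated-measures model; if both, under AR1, the 12-month standard error is too small

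*SAP*

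**What the plan says.** SAP 10.1 (Primary Efficacy Analyses) sets out two mixed models for each co-primary domain.

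The first is a 12-month model with a practice random effect. Baseline SIS enters it as a covariate only.

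The second is a repeated-measures model. It is introduced for the missing-data analysis, conditional on there being a cluster effect. Its fixed part includes "baseline covariates (baseline score, gender, cluster size, time since last stroke at consent"). The time index k is defined as the 6- and 12-month scores. The distribution statement nevertheless lists three responses, the first at baseline, and describes the intercept as the "intercept which represents the average baseline SIS score for person" i. The residual covariance starts as AR1, and the 12-month treatment coefficient is marked as primary.

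SAP 11 (Missing Data) says that the repeated-measures mixed models are for the co-primary endpoints and that "The outcome variable will include baseline, 6months and 12months outcomes". It specifies a participant random effect, time as a factor, autocorrelated residuals (unstructured by arm if the data allow) and further baseline covariates that it does not name.

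Protocol 10.2 leaves the full detail to the SAP, so nothing elsewhere settles the matter.

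**The concern.** An analyst who takes the covariate list and response vector of SAP 10.1 together with the outcome definition of SAP 11 fits baseline SIS on both sides of the equation. The baseline covariates carry no visit index, so one coefficient serves all visits. In the baseline row the covariate is the response. That row pulls the coefficient towards 1 and leaves very small residuals. A structure with one variance for all visits averages these residuals with the follow-up residuals. The standard error of the 12-month effect then rests on a variance that is too low.

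At stake are the width of the 97.5% intervals and the 2.5% error rate allotted to each co-primary, for a coefficient that the SAP itself marks as primary.

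**Working it through.** **1. The texts side by side**

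| Place | Baseline as covariate | Baseline as outcome |
|---|---|---|
| 10.1, covariate list | yes | – |
| 10.1, index k | – | no (6 and 12 months) |
| 10.1, response vector and intercept | – | yes |
| 10.1, mean vector | no such term shown | yes |
| 11 | not named | yes |

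Three models can be read from this: covariate only, outcome only, or both.

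**2. The plan's own figure**

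The only related figure in the documents is the power in SAP 7. Inputs: "With 23 clusters per arm and an average of 20 patients per cluster", "intra-class correlation of 0.03", "a typical coefficient of variation of the cluster size of 0.65", "2.5% significance (adjusted to 2.5% because of the use of two co-primary outcomes") taken as two-sided, and the ability to "detect an effect size of 0.33 with at least 90% power on the co-primary outcomes".

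- After 20% loss, m = 16. Design effect = 1 + [(1 + 0.65²) × 16 − 1] × 0.03 = 1.653.
- Effective n per arm = 23 × 16 / 1.653 = 222.7.
- Power = Φ(0.33 × √(222.7/2) − 2.241) = 89.3%.
- With m = 20, the design effect is 1.824 and the power 92.9%.

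The stated figure is reproduced to within a point. The documents give no SD, standard error or baseline-to-follow-up correlation, so everything below rests on assumed correlations.

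**3. The mechanism by hand**

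Take unit variance at each visit, a visit factor (as in SAP 11), one common baseline slope b and one residual variance. Ignore the practice effect and the residual correlation. Let r6 and r be the correlations of baseline with the 6- and 12-month scores.

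- b = (1 + r6 + r)/3
- Residual variances: v0 = (1 − b)², v6 = 1 − 2b·r6 + b², v12 = 1 − 2b·r + b²
- Pooled variance: a = (v0 + v6 + v12)/3
- Model SE = √(2a/n); true SD = √(2·v12/n); n = 23 × 16 = 368 per arm
- Rejection rate = 2[1 − Φ(2.241 × SE/SD)]

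For r6 = r = 0.5: b = 0.667, v0 = 0.111, v6 = v12 = 0.778, a = 0.556. The SE is 0.0549 and the SD 0.0650. The ratio is 0.845 and the rejection rate 5.8%. Simulation of this case with an ICC near 0 gave 0.0551, 0.0662, 0.83 and 6.5%.

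**4. Simulation of the double-use model**

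Settings: 400 trials each, no treatment effect, 46 practices of 16, ICC 0.03, complete data, REML, AR1 with common variance. In the AR1 pattern, r6 = √r.

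| Pattern | r | SE/SD by hand | SE/SD simulated | Rejection by hand |
|---|---|---|---|---|
| Compound-symmetric | 0.3 | 0.86 | 0.87 | 5.4% |
| | 0.5 | 0.85 | 0.86 | 5.8% |
| | 0.7 | 0.83 | 0.82 | 6.2% |
| | 0.8 | 0.83 | 0.78 | 6.4% |
| AR1 | 0.3 | 0.78 | 0.78 | 7.9% |
| | 0.5 | 0.76 | 0.76 | 9.1% |
| | 0.7 | 0.73 | 0.74 | 10.1% |
| | 0.8 | 0.72 | 0.72 | 10.5% |

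Simulated rejection was 5% to 10%. The Monte Carlo error of each empirical SD is about 3.5%.

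Variations:

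- A participant random intercept in place of AR1 gave a shortfall of 13% to 29%.
- An ICC near 0 (compound-symmetric, r = 0.5 and 0.7) gave 11% to 17%. The 11% is partly noise: by hand that case gives 17%, and the 12-month baseline-as-covariate model in the same runs had a ratio of 1.10.
- A separate simulation gave ratios of 0.69 to 0.80 and rejection of 6.5% to 13%. There, baseline used once gave 0.88 to 0.95, so not all of that shortfall comes from the double use.
- An unstructured covariance mostly sent the baseline slope to 1 and the baseline residual variance to its boundary. Across eight settings the mean model SE was 1.3 to 4.0 times the empirical SD, which is unreliable rather than too small.

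**5. Baseline used once (ICC 0.03)**

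SE/SD was 0.98 to 1.07 for the 12-month model, 0.98 to 1.06 for 6 and 12 months with baseline as covariate (unstructured), and 0.95 to 1.04 for baseline as outcome only (unstructured). Type I error was about 1% to 4.5%. Baseline as outcome under AR1 gave ratios of 1.15 to 1.27 in four compound-symmetric settings, so AR1 can also mislead once the double use is removed.

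**The case against.** The double-use model is not written out in full in either section. The definition of k points to covariate only, and the mean vector in SAP 10.1 points to outcome only. SAP 11 does not name the baseline score as a covariate. The covariate list repeats that of the 12-month model and may simply have been carried over. The equations were also read from a PDF, so fine points of their layout prove little. All of this stands, and it is why the point is a conflict between passages and not a settled error.

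A reader might infer that the co-primary tests as such run at 5% to 13%. The documents do not support that. The 12-month model uses baseline only as a covariate, and the repeated-measures model is introduced for missing data. Sections 8.2.1 and 10.1 also restrict the primary population in a way that fits the 12-month model. Against this, SAP 10.1 marks the repeated-measures coefficient as primary, and SAP 11 ties such models to the co-primary endpoints. The role of the model is therefore open, not peripheral.

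A reader might also want one figure for the shortfall, such as 20%. No single value can be derived. It depends on a correlation that the documents do not give, and the effect takes another form under the unstructured option.

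**Conclusion.** The SAP does not say consistently whether baseline SIS is an outcome, a covariate or both in the repeated-measures model, and one natural reading gives wrong error bars. Under that reading with common-variance AR1, the standard error of the 12-month effect is roughly 11% to 30% too small, and the type I error is about 5% to 13% against 2.5%.

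The range rests on assumed baseline-to-12-month correlations of about 0.3 to 0.8, the SAP 7 design, a visit factor that the SAP 10.1 equation does not show, equally spaced visits, equal clusters of 16 and no missing data. The direction was the same in every common-variance setting, and the hand calculation agrees. Moving to an unstructured covariance does not rescue the double-use model. The 12-month model in SAP 10.1 is sound on this point.

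**What to change.** Use baseline SIS once, in one of two forms:

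- (a) outcomes at 6 and 12 months, with baseline SIS as a covariate; or
- (b) outcomes at baseline, 6 and 12 months, with a common baseline mean across arms and the baseline score removed from the covariate list.

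Make an unstructured covariance the first choice in either form. Write the same model in SAP 10.1 and SAP 11, and make the index k match the response vector. State whether the 12-month model or the chosen repeated-measures model gives the primary estimate, and move the primary label accordingly.

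The cost is SAP wording. No data collection, sample size or patient procedure changes.

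### The missing-data model in SAP 10.1 has no visit effect, so its β₂ is not the 12-month treatment difference if scores drift in both arms, and SAP 11 does not repair it

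*SAP*

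**What the plan says.** SAP 10.1 contains two kinds of model. The first takes one 12-month score per patient, with treatment, baseline covariates and a practice random effect. The second is a repeated-measures model, introduced with "For missing data analysis the following model will be fitted if there is a cluster effect". After a covariate term that carries no visit index, its right-hand side continues "\beta_1 X_{1ij6} + \beta_2 X_{1ij12} + u_j" and ends with a residual that is initially AR(1). β₂ is defined as the "difference in score between intervention and control groups at 12 months (primary", and β₀ as the "intercept which represents the average baseline SIS score for person" i.

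The visits are given in two ways. In the list of symbols, k means "6 month and 12 follow-up scores", and the baseline score is among the covariates. The mean vector printed below that list has three entries, for 0, 6 and 12 months.

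SAP 11 describes a mixed model for the same purpose. It states: "The outcome variable will include baseline, 6months and 12months outcomes". It also says that "the fixed factors will be time, included as a factor variable, and treatment indicator". It names no treatment-by-time term, and its random effect is for the participant, not the practice.

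**The concern.** A treatment-by-visit term measures the difference between arms at that visit only if the model also lets the control mean move from visit to visit. The covariates listed under X₀ (baseline score, gender, cluster size, time since last stroke at consent) are fixed for each patient and cannot do this. The 10.1 equation therefore holds the control mean level, and β₂ compares the intervention arm at 12 months with a blend of control scores from several visits.

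Any drift shared by both arms then enters β₂ with its own sign: it can mimic an effect, shrink a real one or enlarge it. Such drift is foreseeable. SAP 12 notes that both co-primary scores "may be affected by this event, a sensitivity analysis will be conducted by repeating the primary analyses" with a lockdown indicator, and for some patients lockdown will fall between the 6- and 12-month visits. That indicator has one value per patient, so it does not stand in for a visit effect.

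At stake is the analysis meant to show whether the primary result survives missing data. If its coefficient estimates something else, agreement or disagreement with the primary result cannot be interpreted.

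**Working it through.** **Inputs.** From SAP 7: 23 practices per arm, mean 20 patients, 20% loss (16 analysed), ICC 0.03, CV of cluster size 0.65, 2.5% significance, effect size 0.33. From SAP 10.1: the equation and AR(1) residuals. Assumed, because the documents give no figure: the shared change d in SD units, within-patient correlation ρ from 0 to 0.9, a two-sided test and, in the leakage calculations, complete data and equal cluster sizes.

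**The plan's own figure.** The plan states no figure for change over time. The design inputs can be checked against the stated power. Design effect = 1 + ((1 + 0.65²) × 16 − 1) × 0.03 = 1.653. Effective n per arm = 23 × 16 / 1.653 = 222.7. Power by normal approximation = 89.3%, close to the stated 90%.

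**Outcomes at 6 and 12 months (10.1's definition of k).** Let there be no treatment effect and let both arms move from 0 to d between the visits. The control arm has one mean parameter a, and by symmetry it is estimated as (0 + d)/2 = d/2. The intervention arm has its own parameter at each visit:
- β₁ = 0 − d/2 = −d/2
- β₂ = d − d/2 = +d/2

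This share was exactly one half for every ρ and ICC tried. If both arms have already moved by d at 6 months and stay there, a = d and β₂ = 0.

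**Outcomes at 0, 6 and 12 months (the three-entry vector and SAP 11).** Now a is estimated from three control visits and the intervention baseline. With ICC 0 and AR(1) correlation ρ, generalised least squares gives β₂/d as:
- step change complete by 6 months: 1 − (1 − ρ²)(2 − ρ)/4
- linear change: 1 − (1 − ρ²)(3 − ρ)/8

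At ρ = 0.6 these are 1 − 0.64 × 1.4/4 = 0.776 and 1 − 0.64 × 2.4/8 = 0.808. Numerical results, including the practice effect:

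| ρ | ICC | Step | Linear |
|---|---|---|---|
| 0 | 0 | 0.500 | 0.625 |
| 0.6 | 0 | 0.776 | 0.808 |
| 0.6 | 0.03 | 0.859 | 0.880 |
| 0.9 | 0.03 | 0.966 | 0.967 |

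**Simulation check** (60 maximum-likelihood fits per setting, ρ = 0.6, ICC 0.03, no treatment effect). With three visits and a linear change of 0.1 or 0.2 SD, mean β₂ was 0.086 or 0.173. With two visits and the same change between 6 and 12 months, it was 0.05 or 0.10. Rejection at the nominal 2.5% was about 35% and 88% with three visits, and about 7% and 13% with two. These rates rest on few runs and on assumed drifts.

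**With a visit factor added**, the expected β₂ is 0 on both readings for every ρ and ICC tried. In the simulations it lay between −0.014 and 0.001 SD (Monte Carlo SE about 0.01).

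**The SAP 11 model.** Shared drift does not bias it. But one treatment coefficient spans all visits, including a baseline taken before randomisation. With complete data and equal visit weights it estimates (0 + δ₆ + δ₁₂)/3, where δ is the true difference at each visit. If both equal 0.33, that is 0.66/3 = 0.22, which is not the 12-month effect.

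**The case against.** The strongest reply is that this is not the primary model. SAP 10.1 reserves the equation for missing data and makes it conditional on a cluster effect. SAP 8.2.1 restricts the co-primary analysis to patients with baseline and 12-month data. Protocol 10.2 describes one mixed model per outcome, and SAP 17 declares no change from it. The bracketed word primary may simply mark 12 months as the primary time point. This stands: the single-time-point model needs no visit term. The wording still leaves room for error, because 10.1 speaks of the primary model as yet to be decided and SAP 11 says that mixed models will analyse the repeated co-primary scores.

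The second reply is that SAP 11 does include time. It does, so the SAP contradicts itself rather than overlooking time throughout. Without a treatment-by-time term, however, SAP 11 does not rescue the 12-month contrast.

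A reader might infer that any shared change biases β₂. On 10.1's own definition of k that is not so: a change equal at 6 and 12 months leaves it untouched. A reader might also take the 35% and 88% rejection rates as the trial's false-positive risk. The documents do not support that. Those rates pair SAP 11's outcome set with 10.1's missing visit term, under drifts that appear nowhere in the plan.

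Nor does the mean vector prove that control means are held equal. Read literally, it gives controls β₀, β₀ + β₁ and β₀ + β₂, which contradicts the equation. Its layout may have suffered in conversion from PDF, so the point rests on the equation.

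**Conclusion.** The point holds for the repeated-measures model in SAP 10.1. As printed, its β₂ is not the 12-month difference if scores change over time in both arms. It takes half of a shared 6-to-12-month change when only those visits are outcomes. It takes roughly 50% to 97% of a shared change from baseline when baseline is also an outcome. These shares depend on the assumed correlation, ICC and shape of change, with complete data and equal cluster sizes. The size of any shared change is unknown, and with none there is no bias.

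The single-time-point 12-month analysis is unaffected, so this is no finding against the headline result if that model is the one reported. SAP 10.1 and SAP 11 differ on the visit effect, on treatment-by-time terms and on the random effect. Section 10.1 is itself inconsistent about whether baseline is an outcome. Neither section specifies a model that delivers the stated 12-month effect, so this is more than a matter of added detail.

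**What to change.** Write one missing-data model and refer to it in both SAP 10.1 and SAP 11:

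- visit as a factor;
- treatment-by-visit terms at 6 and 12 months;
- baseline SIS score and the other pre-specified covariates;
- a practice random effect and a within-patient covariance.

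State whether baseline is an outcome or a covariate. If it becomes an outcome, remove it from the covariate list and give no treatment term at that visit. Correct the mean vector so that the treatment indicator multiplies β₁ and β₂. State that the single-time-point 12-month model is the primary analysis and that the word primary beside β₂ marks only the time point.

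The cost is SAP wording and a few model terms, with no new data or patients. It should be settled before the analysis is run.
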